7. STUDY CALENDAR & EVALUATIONS

Study Evaluations Cycle = 21 days for Pembrolizumab Cycle = 5 days for HD IL-2	Screening	Cycles 1-2 Pembrolizumab (P)	End of Cycle 2 Pembro	Cycle 1 HD IL2	Cycle 2 HD IL2	Safety follow up visit ¹¹	Long-term Follow up ¹²
	-28 days	Day 1 (± 3 days)	Day 21 (± 3 days)	Days 1-5	Days 15-19	28 days post last dose (± 7 days)	Every 3 months (±14 days)
REQUIRED ASSESSMENTS							
Informed Consent/HIPPA authorization	X						
Medical History ¹	X						
Diagnosis and Staging ²							
Physical Exam	X	X	X	X	X	X	
Vital signs and ECOG Performance Status ³	X	X	X	X	X	X	
AEs & concomitant medications	X	X	X	X	X	X	
LABORATORY ASSESSMENTS							
Complete Blood Cell Count with diff (CBC)	X	X ¹⁰	X	X	X	X	
Comprehensive Metabolic Profile (CMP)	X	X ¹⁰	X	X	X	X	
PT/INR and aPTT	X	X ¹⁰					
Thyroid Function (TSH, T4, free T3)	X		X				
Vitamin D level	X						
Pregnancy test (serum or urine) (WOCBP) ⁴	X	X ⁴					
Urinalysis	X	X ¹⁰	X		X		
DISEASE ASSESSMENT							
Chest X-ray				X			
CT of chest ⁵	X		X			X	
CT or MRI of abdomen and pelvis ⁵	X		X			X	
CT or MRI Brain ⁵	X		X			X	
TREATMENT EXPOSURE							
Pembrolizumab		X					
HD IL-2				X	X		
SPECIMEN COLLECTION							
Archival Tumor Tissue ⁶	X						
Blood Samples ⁷		X ⁷	X	X	X ⁷		
Stool sample ⁸		X					

Study Evaluations Cycle = 21 days for Pembrolizumab Cycle = 5 days for HD IL-2	Screening	Cycles 1-2 Pembrolizumab (P)	End of Cycle 2 Pembro	Cycle 1 HD IL2	Cycle 2 HD IL2	Safety follow up visit ¹¹	Long-term Follow up ¹²
	-28 days	Day 1 (± 3 days)	Day 21 (± 3 days)	Days 1-5	Days 15-19	28 days post last dose (± 7 days)	Every 3 months (±14 days)
BANKING SAMPLES							
Whole blood, Plasma and PBMCs ⁹		X ⁹	X			X	
FOLLOW-UP							
Survival Status, Subsequent Therapy							X

Key to Footnotes

CBC with differential and platelet to include: Hgb, Hct, WBC, ANC, lymphocyte count, platelets. CMP to include sodium, potassium, chloride, creatinine, blood urea nitrogen; liver function tests (LFTs) to include AST, ALT, total bilirubin, alkaline phosphatase

1: Medical History to include documentation of prior anti-cancer treatment including medications (chemotherapy, checkpoint inhibitors, etc.), radiation, or surgery. A question of how the subject learned about the study will be asked.

2: Diagnosis and staging to include pathology report and Tumor Node Metastasis (TNM) staging.

3: Vital signs to include blood pressure, weight, and height (screening only) and ECOG performance status.

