- 11: The safety follow-up visit should occur when subjects permanently stop study treatment for whatever reasons (toxicity, progression, or at discretion of site investigator) and should be performed 30 days (± 7 days) after the last dose of treatment. Subjects who have an ongoing Grade \geq 2 or serious AE (SAE) at this visit will continue to be followed until the AE resolves to \leq Grade 1 or baseline, deemed clinically insignificant, and/or until a new anti-cancer treatment starts, whichever is earlier.
- 12: Long-term follow up will occur in all subjects after the safety follow up visit. Subjects who discontinue treatment for any reason will be followed every 3 months for 12 months. Follow up may be accomplished via clinic visit, phone call, or other avenues as appropriate.

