9.9.2 Confirmation of Response

To be assigned a status of complete or partial response, changes in tumor measurements must be confirmed by repeat assessments performed no less than four weeks after the criteria for response are first met.

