9.9.5 Objective Response Rate

The objective response rate is the proportion of all subjects with confirmed PR or CR according to RECIST 1.1, from the start of treatment until disease progression/recurrence (taking as reference for progressive disease the smallest measurements recorded since the start of treatment).

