12 STATISTICAL METHODS

12.1 Study Design

The primary objective of this single arm Phase II trial is to assess the response rate [complete response (CR) + partial response (PR)] of sequential therapy of pembrolizumab followed by HD IL-2 in subjects with stage IV malignant melanoma. Response assessment will be performed using revised RECIST guideline (version 1.1). The trial will consist of two phases. In the first phase of this trial, therapy will be initiated with pembrolizumab followed by HD IL-2 therapy. Pembrolizumab 200 mg will be given every 3 weeks for 2 doses (cycles). Staging will occur approximately 20 days after the last treatment dose (i.e., Day 21 [+3 days] of Cycle 2). Then subjects will receive HD IL-2 for 2 cycles, Cycle 2 separated from Cycle 1 by 9 days (one course). Subjects are hospitalized during each cycle which consists of up to 14 infusions over a 5 day period (3 infusions/day spaced 8 hours apart). Four weeks after the last HD IL-2 administration of Cycle 2, the subjects will be restaged (i.e., their disease status reassessed). For subjects with progressive disease as revealed by the restaging, they will be followed for OS up to one year from initiation of the first treatment (pembrolizumab) of the study. For subjects with CR, PR, and SD, scans will be performed at 3-month intervals until disease progression or up to a year after initiation of the first treatment (with pembrolizumab) on study. For the subjects who progress, although they will be taken off the study they will be followed for OS up to one year from initiation of the first treatment (pembrolizumab) of the study.

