12.2 Endpoints and Analyses

12.2.1 Primary Endpoint

The primary endpoint of this single arm Phase II trial is to assess the response rate [complete response (CR) + partial response (PR)] of sequential therapy of pembrolizumab followed by HD IL-2 in subjects with stage IV malignant melanoma, using revised RECIST guideline (version 1.1). Response rate will be computed with associated 95% confidence intervals constructed from the exact Binomial method.

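### The study calendar schedules none of the 3-monthly follow-up scans that Section 12.1 requires for subjects with CR, PR or SD

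*Combined protocol and SAP*

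**What the plan says.** All references are to the combined protocol and SAP.

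- **Section 12.1, restaging after HD IL-2:** "Four weeks after the last HD IL-2 administration of Cycle 2, the subjects will be restaged".
- **Section 12.1, later imaging:** "For subjects with CR, PR, and SD, scans will be performed at 3-month intervals until disease progression or up to a year", the year running from the first pembrolizumab dose.
- **Section 7, study calendar:** the CT and MRI rows are marked at screening, at the end of pembrolizumab Cycle 2 and at the safety follow-up visit. The 3-monthly long-term column has one marked row: "Survival Status, Subsequent Therapy".
- **Section 7, footnote 5:** it names two post-treatment scans, one at the end of pembrolizumab and one after HD IL-2 Cycle 2.
- **Section 7, footnote 12:** long-term follow-up covers every subject. "Follow up may be accomplished via clinic visit, phone call, or other avenues as appropriate". No exception is made for subjects still in response or stable.
- **Sections 9.9.7 and 12.2.2:** subjects without progression are censored for PFS at their last disease evaluation, and a Kaplan-Meier PFS rate is planned at 1 year ± 3 months.
- **Section 9.9.2:** "changes in tumor measurements must be confirmed by repeat assessments performed no less than four weeks after the criteria for response are first met".
- **Section 9.9.5:** "The objective response rate is the proportion of all subjects with confirmed PR or CR according to RECIST 1.1".
- **Section 12.2.1, primary endpoint:** "to assess the response rate [complete response (CR) + partial response (PR)] of sequential therapy of pembrolizumab followed by HD IL-2". It does not mention confirmation; nor do 2.2.1 and 12.5.

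**The concern.** Sites commonly book visits from the calendar, whereas the 3-monthly imaging rule stands only in the statistics section. A site can satisfy the calendar and its footnotes by telephoning a responding subject every 3 months and never scanning again.

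The firmer consequence is for PFS. Subjects who are alive without known progression would be censored at the post-HD IL-2 scan. Deaths would still be found through the survival checks. Beyond that scan, the PFS curve at such sites would therefore rest on deaths and on whatever unscheduled imaging happened to be done. The planned PFS rate around 1 year would not be supported by scheduled disease assessment.

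The second consequence is conditional. If only confirmed responses count for the primary endpoint, a response first met at the post-HD IL-2 scan has no later calendar scan to confirm it. That is the first scan that can show the effect of the whole sequence.

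**Working it through.** **The plan's own figure.** The plan gives no figure for scan timing. Its stage 1 early-termination probability reproduces: the sum over x = 0 to 3 of C(11,x) × 0.26^x × 0.74^(11−x) is 0.6854, against 0.685 stated in 12.3. Nothing below alters that design calculation.

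**Inputs for the timeline.**
- Day 1 is the first pembrolizumab dose. Two 21-day cycles (5.1) put the end-of-pembrolizumab scan on day 42.
- HD IL-2 Cycle 2 ends on Day 19 of the course (5.2), which is the start day + 18.
- The post-HD IL-2 scan is 28 days later (calendar safety visit; four weeks in 5.2 and 12.1).
- The PFS window opens at month 9: 9 × 365.25 / 12 ≈ day 274.
- No section fixes the HD IL-2 start. I assume day 43 to 57 without delay.

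**Formulas.** Last calendar scan = HD IL-2 start + 18 + 28. Gap = 274 − last calendar scan.

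| Case | HD IL-2 start | Last calendar scan | Gap to day 274 |
|---|---|---|---|
| No delay, earliest assumed start | 43 | 89 | 185 days (6.1 months) |
| No delay, latest assumed start | 57 | 103 | 171 days (5.6 months) |
| HD IL-2 starts 12 weeks late (43 + 84) | 127 | 173 | 101 days (3.3 months) |
| Same, plus 83 days between HD IL-2 cycles | 127 | 173 + 83 = 256 | 18 days |

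The delay rows use the 12-week limits in 6.2.1 and in the section on protocol therapy discontinuation, assuming that the first limit also covers the first HD IL-2 cycle. The visit's ±7 days moves each gap by up to 7 days either way. If pembrolizumab Cycle 2 were also delayed by 83 days, the last scan would fall on day 256 + 83 = 339, inside the window. Censoring before the window is therefore the ordinary case, but not the outcome under every permitted combination of delays.

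**What 12.1 adds.** Scans at 91-day steps after day 89 fall on days 180, 271 and 362. After day 103 they fall on days 194 and 285; the next, day 376, is past one year. That is two or three scans which the calendar does not show. In each no-delay case one of them (day 362 or day 285) lies inside the PFS window.

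**Confirmation.** A response first met on day 42 can be confirmed at the post-HD IL-2 scan: 89 − 42 = 47 days, or 103 − 42 = 61 days, both above the 28-day minimum. A response first met on day 89 or 103 has no later calendar scan. Under 12.1 the next scan is 91 days later (day 180 or 194). Even then, a response first met at the last 12.1 scan would still need the repeat assessment in 9.9.2.

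**The case against.** **The calendar omits the scans; it does not forbid them.** Footnote 12 permits a phone call for a column whose only marked row needs no visit, and 12.1 is worded as a requirement. This stands: a reader might infer that the calendar overrides 12.1, but nothing says so. Equally, no section says that 12.1 governs, so a site can omit the scans while complying with the calendar.

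**A blank cell is imperfect evidence.** In the text available, the row for diagnosis and staging has no mark in any column, so marks may be missing elsewhere. That is fair, but the point does not rest on blank cells alone. Footnote 5 lists no later scans, although its wording is incomplete, and footnote 12 allows contact without imaging.

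**The primary endpoint may not be touched.** The opening of Section 5 places response assessment after pembrolizumab and again after HD IL-2, and the calendar schedules both scans. On that reading the response rate needs nothing further. Sections 9.9.2 and 9.9.5 point the other way. The effect on the primary endpoint is therefore arguable. A reader might go on to infer a loss of power under the two-stage rule. The documents do not support a figure, because no section gives the share of responses first met after HD IL-2.

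**Related timings.** A reader might take the +9 days in footnote 5 as a scan window conflicting with the four-week restaging. That depends on one reading of text with an unmatched bracket; read as a tolerance on the four-week scan, it conflicts with nothing. The calendar's 28 ± 7 days, footnote 11's 30 ± 7 days and four weeks all include day 28 and are compatible. The 12 months in footnote 12 has no stated start, so it is ambiguous rather than shown to contradict 12.1.

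**Conclusion.** The inconsistency is real and should be fixed. Section 12.1 requires 3-monthly scans for subjects with CR, PR or SD; the calendar and footnotes 5 and 12 schedule none; no section settles which applies.

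For PFS, a site following the calendar would have its living, progression-free subjects censored about 171 to 185 days before the window opens if treatment is not delayed. The gap shrinks to about 101 days if HD IL-2 starts 12 weeks late, and further with stacked delays. A reader might treat six months as a fixed gap; it is only the no-delay case, and it rests on the assumed HD IL-2 start of day 43 to 57. How many sites would work from the calendar rather than 12.1 is unknown.

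For the response rate, the missing confirming scan matters only if 9.9.2 and 9.9.5 apply to the primary endpoint. The size of that effect is unknown, and no loss of power is claimed.

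**What to change.** 1. In the calendar's long-term column, mark the 3-monthly disease-assessment scans that 12.1 requires for subjects with CR, PR or SD, ending at progression or one year from first pembrolizumab. Section 12.1 does not name the modality, so the marked rows should make it explicit.
2. Add these scans to footnote 5, with a cross-reference to the repeat assessment in 9.9.2.
3. State in footnote 12 that phone contact suffices for survival status and subsequent therapy but does not replace a scheduled scan.
4. Secondary: complete the +9 days text in footnote 5 so that it agrees with the four-week restaging in 5.2 and 12.1, and state when footnote 12's 12 months starts and ends, consistently with 12.1. Footnote 11's visit window needs no change.

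The cost is wording in one calendar column and two footnotes. No scans are added beyond those that 12.1 and 9.9.2 already require.

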8. BIOSPECIMEN STUDIES AND PROCEDURES

8.1 Correlate PD-L1 expression in archived diagnostic tumor tissue with best clinical response (revised RECIST criteria) and treatment outcome in subjects with stage IV malignant melanoma

Expression of PD-L1 in archived diagnostic tumor tissue will be determined by IHC by referring laboratory using anti-PD-L1 antibody clone 22C3, and will be correlated with clinical response assessed by imaging. Unstained slides are to be submitted; a tumor block is not acceptable.

8.2 Correlate the change in soluble PD-L1 and arginine levels in plasma during therapy with best clinical response (revised RECIST criteria) and treatment outcome in subjects with stage IV malignant melanoma

Whole blood for serum submission will be collected pre-dose Cycle 1 Day 1 of pembrolizumab, and on Cycle 2 Day 21 (+3 days) of pembrolizumab. Blood samples for these levels will also be collected at the end of each of the HD IL-2 cycles; End of Cycle 1 sample will be drawn prior to dosing Cycle 1 Day 5 (+3 days). The end of Cycle 2 sample will be drawn (+ 9 days) at the end of Cycle 2 Day 19 for analysis of soluble PD-L1 and arginine levels. Change in soluble PD-L1 and arginine levels as a result of treatment will be examined in relation to the best clinical response (RECIST, v1.1) and treatment outcome.

8.3 Correlate Th1/Th2 ratio and MDSCs in peripheral blood during therapy with best clinical response (revised RECIST criteria) and treatment outcome in subjects with stage IV malignant melanoma

Whole blood for serum submission will be collected pre-dose Cycle 1 Day 1 of pembrolizumab, and on Cycle 2 Day 21 (+3 days) of pembrolizumab. Blood samples for these levels will also be collected at the end of each of the HD IL-2 cycles; End of Cycle 1 sample will be drawn prior to dosing Cycle 1 Day 5 (+3 days). The end of Cycle 2 sample will be drawn (+ 9 days) at the end of Cycle 2 Day 19 for analysis of Th1/Th2 ratio levels and MDSC quantification. Change in Th1/Th2 ratio and MDSCs levels as a result of treatment will be examined in relation to the best clinical response (RECIST, v1.1) and treatment outcome.

8.4 Correlate intestinal microbiome at baseline with best clinical response (revised RECIST criteria) and treatment outcome in subjects with stage IV malignant melanoma

Samples of stool will be collected prior to pembrolizumab treatment in a stool collection tube per manufacturer's guidelines. Microbial DNA will be isolated using the Invitek PSP® Spin Stool DNA Plus Kit (with lysis enhancer) as described by the manufacturer [29]. Subsequent microbiome characterization will be performed after study complete accrual using Illumina 16S Metagenomic sequencing protocol.

8.5 Correlative samples for future unspecified cancer related studies

Subject consent will be obtained for additional samples (whole blood, plasma and PBMCs) to be collected and banked for future unspecified cancer related research. Samples will be collected at baseline (pre-dose Cycle 1 Day 1 of pembrolizumab) and on Cycle 2 Day 21 (+3 days) of pembrolizumab. This sample will also be collected about 4 weeks after the last dose of HD IL-2 (safety visit). These samples will be banked at HCRN.

8.5.1 Storage of Biospecimens

Remaining specimens once protocol described biospecimen-based studies are complete will be stored for future unspecified cancer related research. Permission for this will be obtained from subjects in the informed consent.

8.5.2 Confidentiality of Biospecimens

Samples that are collected will be identified by a subject's sequence ID number assigned at the time of registration to the trial. Any material issued to collaborating researchers will be anonymized and only identified by the subject's sequence ID number.

9. CRITERIA FOR DISEASE EVALUATION

Response assessments will be made using RECIST v1.1 [30], allowing additional comparisons among these criteria for disease response assessment. The same measurable and non-measurable lesions will be followed by RECIST v1.1. Disease progression will be determined using RECIST v1.1 criteria.

9.1 Measurable Disease

The presence of at least one measurable lesion. If the measurable disease is restricted to a solitary lesion, its neoplastic nature should be confirmed by cytology/histology.

9.2 Measurable Lesions

Measurable lesions are defined as the presence of at least one measurable lesion. Measurable lesions are defined as those that can be accurately measured in at least one dimension (longest diameter to be recorded) as ≥ 20 mm by chest x-ray, as ≥ 10 mm with CT scan, or ≥ 10 mm with calipers by clinical exam. All tumor measurements must be recorded in millimeters (or decimal fractions of centimeters).

9.2.1 Malignant Lymph Nodes

To be considered pathologically enlarged and measurable, a lymph node must be ≥ 15 mm in short axis when assessed by CT scan (CT scan slice thickness recommended to be no greater than 5 mm). At baseline and in follow-up, only the short axis will be measured and followed.

9.3 Non-measurable Lesions

All other lesions (or sites of disease), including small lesions (longest diameter <10 mm or pathological lymph nodes with ≥ 10 to <15 mm short axis), are considered non-measurable disease. Bone lesions, leptomeningeal disease, ascites, pleural/pericardial effusions, lymphangitis cutis/pulmonitis, inflammatory breast disease, and abdominal masses (not followed by CT or MRI), are considered as non-measurable.

NOTE: Cystic lesions that meet the criteria for radiographically defined simple cysts should not be considered as malignant lesions (neither measurable nor non-measurable) since they are, by definition, simple cysts. 'Cystic lesions' thought to represent cystic metastases can be considered as measurable lesions, if they meet the definition of measurability described above. However, if non-cystic lesions are present in the same subject, these are preferred for selection as target lesions.

9.4 Target Lesions

All measurable lesions up to a maximum of 2 lesions per organ and 5 lesions in total, representative of all involved organs, should be identified as **target lesions** and recorded and measured at baseline. Target lesions should be selected on the basis of their size (lesions with the longest diameter), be representative of all involved organs, but in addition should be those that lend themselves to reproducible repeated measurements. It may be the case that, on occasion, the largest lesion does not lend itself to reproducible measurement in which circumstance the next largest lesion which can be measured reproducibly should be selected. A sum of the diameters (longest for non-nodal lesions, short axis for nodal lesions) for all target lesions will be calculated and reported as the baseline sum diameters. If lymph nodes are to be included in the sum, then only the short axis is added into the sum. The baseline sum diameters will be used as reference to further characterize any objective tumor regression in the measurable dimension of the disease.

9.5 Non-target Lesions

All other lesions (or sites of disease) including any measurable lesions over and above the 5 target lesions should be identified as **non-target lesions** and should also be recorded at baseline. Measurements of these lesions are not required, but the presence, absence, or in rare cases unequivocal progression of each should be noted throughout follow-up.

9.6 Evaluation of Target Lesions

NOTE: In addition to the information below, also see section 4.3.2 in the international criteria proposed by the Response Evaluation Criteria in Solid Tumors (RECIST) Committee, version 1.1 (Eur J Cancer 45;2009:228-247) for special notes on the assessment of target lesions.

Complete Response (CR)	Disappearance of all target lesions. Any pathological lymph nodes (whether target or non-target) must have reduction in short axis to <10 mm.
Partial Response (PR)	At least a 30% decrease in the sum of the diameters of target lesions, taking as reference the baseline sum diameters
Progressive Disease (PD)	At least a 20% increase in the sum of the diameters of target lesions, taking as reference the smallest sum on study (this includes the baseline sum if that is the smallest on study). In addition to the relative increase of 20%, the sum must also demonstrate an absolute increase of at least 5 mm. (Note: the appearance of one or more new lesions is also considered progressions).
Stable Disease (SD)	Neither sufficient shrinkage to qualify for PR nor sufficient increase to qualify for PD, taking as reference the smallest sum diameters while on study

9.7 Evaluation of Non-Target Lesions

Complete Response (CR)	Disappearance of all non-target lesions and normalization of tumor marker level.
Incomplete Response/Stable Disease	Persistence of one or more non-target lesion(s) and/or maintenance of tumor marker level above the normal limits
Progressive Disease (PD)	Appearance of one or more new lesions and/or unequivocal progression of existing non-target lesions.

Although a clear progression of “non-target” lesions only is exceptional, the opinion of the site investigator should prevail in such circumstances, and the progression status should be confirmed at a later time by the sponsor investigator.

